## 2.5. Research Visit 2:

Both groups will complete the self-evaluation questionnaires Perceived Stress Scale-Motor and Motor Function Survey.

### 2.5.1. Procedures for the PD-neurofeedback group:

There will be no interference with the medication schedule. Subjects will take their dopaminergic medications as scheduled.

#### 2.5.1.1. Imagery Practice Session:

The aim of this session is to determine each subject's motor repertoire, identify their motor difficulties, and familiarize them with mindfulness body scan and motor imagery practices. Subjects will be informed about both practices and will be given time to ask questions. Subjects will be primed to experience body awareness by engaging in a mindfulness body scan practice during which they will listen to an audio recording guiding them to pay attention to sensations in different body parts. Subsequently, audio-recorded scripts with detailed descriptions of basic movements will be provided for each subject to practice. These scripts are based on the kinesthetic imagery component of the standard motor imagery questionnaires (Kinesthetic and Visual Imagery Questionnaire and Movement Imagery Questionnaire-3). Subjects will first perform the movements (e.g., raise your knee, lift up your arm, tap

your foot, etc.), then imagine performing the movements while at the same time focusing on the sensations (e.g., proprioceptive, kinesthetic, interoceptive) evoked by the movements. Finally, subjects will practice guided kinesthetic motor imagery of whole body complex movements (e.g., walking, running, swimming, calisthenics) on their own. Subjects will be instructed to focus on the imagined bodily felt sense that the movements in these motor imagery tasks evoke.

### 2.5.1.2. Scanning:

#### 2.5.1.2.1. Resting-State fMRI:

[figure not shown]
After the routine anatomical scan for localization (5 min), fMRI scans will be collected during resting-state for 10 min. Subjects will be instructed to keep their eyes closed and let their mind wander without focusing on a specific thought.

#### 2.5.1.2.2. Neurofeedback-Guided Motor Imagery Scans:

##### Neurofeedback Paradigm:

Subjects will practice the kinesthetic motor imagery of complex movements as described in Section 2.5.1.1. in the scanner during neurofeedback learning.

A night sky picture on the screen will instruct subjects to engage in motor imagery for 40 s. This picture with subdued visual input was chosen to minimize interference during imagery. Subjects will be told not to change strategies within a block. The right insula-dorsomedial frontal cortex functional connectivity strength will be computed during the 40-s task block and presented to the subject in the form of a bar plot for 8 s at the end of the block to provide neurofeedback (blue bar: negative, red bar: positive neurofeedback) (Figure 3B). The magnitude of the bar will reflect the strength of the functional connectivity, and subjects will be instructed to increase this. There will be five motor imagery task blocks followed by feedback in each session. Each subject will complete a total of 6-7 sessions.

**Fig.3. A.** Group activations during the **heart-beat counting task** shown on a coronal slice. Color bar: t values ( $p < 0.001$ , uncorrected, cluster size: 10 voxels). dmFC: Dorsomedial frontal cortex, Ins: Insula, R: Right. **B:** dmFC and Ins masks are translated into each subject's functional space. Functional scans during motor imagery are collected and preprocessed in real-time. The signal time courses averaged across voxels within the masks are correlated with each other (fc: functional connectivity) and the z-transformed correlation values are plotted as bars to provide the neurofeedback.

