The PD-neurofeedback group will perform motor imagery of complex whole body movements (e.g., walking, jogging) in the scanner and focus on the kinesthetic aspects of motor imagery (i.e., body sensations evoked by the imagined movements). This task was chosen based on our preliminary data showing the involvement of the insula (sensation) and dmFC (movement) during kinesthetic motor imagery. Subjects will receive intermittent neurofeedback on their performance. The neurofeedback signal will be computed based on the functional connectivity strength between the subject's right insula and dmFC. The matched PD-control group will perform visual imagery (e.g., shapes, colors) in the scanner and will not receive neurofeedback. Subjects in both groups will also continue their respective imagery training at home. Hypothesis: The PD-neurofeedback group, but not the PD-control group, will

learn to increase the right insula-dmFC functional connectivity strength.

**Aim 2: To examine the effects of neurofeedback-guided motor imagery training on intrinsic functional connectivity of brain networks.**

We will obtain resting-state fMRI scans from the PD-neurofeedback and PD-control groups at baseline and post-training to examine the changes in intrinsic functional connectivity of the right insula and dmFC with the whole brain. *Hypothesis: Post-training, the intrinsic functional connectivity a) between the right insula and dmFC and b) of the right insula and dmFC with the whole brain, specifically with the motor cortical-striatal regions, will be significantly stronger in the PD-neurofeedback compared with the PD-control group.*

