### **1.2. Neurofeedback intervention has the potential to enhance the insula-dmFC functional connectivity strength, thus, improve sustained motor performance in patients with PD.**

Neurofeedback enables subjects to obtain voluntary control over their brain activity through learning. With practice, subjects also learn to regulate the behavior that is associated with this brain activity. For instance, healthy subjects used mental strategies for emotion induction, which led to right insula activation, and learned to modulate this activity with neurofeedback (Caria et al., 2007). fMRI-based neurofeedback has been used successfully in symptom treatment of several neuropsychiatric disorders (e.g., anxiety, depression, addiction) (Hartwell et al., 2013; Scheinost et al., 2013; Young et al., 2014), but reports on its use in PD are scant. Two studies used fMRI-based neurofeedback in patients with PD and demonstrated significant increase in the SMA activity with neurofeedback Subramanian et al., 2011, 2016). This increase was accompanied by a clinically meaningful, but, compared with the control group, statistically insignificant improvement in motor function Subramanian et al., 2016). There is a knowledge gap regarding the mechanism of action, feasibility, and potential efficacy of neurofeedback in PD. We aim to fill this gap by employing a new technique that uses the functional connectivity strength between brain regions, as opposed to the activity in a single brain region, as neurofeedback (Megumi et al., 2015; Koush et al., 2017). In general, this technique is suitable for most neuropsychiatric conditions including PD because they are associated with dysfunction of neural circuits rather than of individual brain areas. It is particularly pertinent for our model that proposes that the insula and dmFC promote sustained intentional movement via their concerted effort. Therefore, we think that this new approach provides a neurobiologically more meaningful measure for use in neurofeedback.

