## 2.3. MRI Scanning Parameters:

Subjects will always be scanned in the morning after they take the first dose of their dopaminergic medication. We will conduct the MRI experiments in a Siemens 3.0 Tesla human research magnet in the MRRC. A 32-channel head coil will be used to collect high-resolution anatomical and echo planar images for fMRI. First, T1-weighted MPRAGE anatomical images (voxel size: 1 x 1 x 1 mm) will be collected for an accurate localization of the fMRI data. T1-weighted FLASH axial images (voxel size: 0.9 x 0.9 x 4 mm, 36 slices, FoV: 224 mm, TR: 300 ms, TE: 2.47 ms, flip angle: 60°) will be collected as an intermediate scan to coregister MPRAGE and echo planar functional images for the neurofeedback sessions. Then, axial, T2-weighted, echo planar functional images will be collected (voxel size: 3.5 x 3.5 x 4 mm, 36 slices, FoV: 224 mm, TR: 2000 ms, TE: 25 ms, flip angle: 90°). The number of acquisitions will be 120 for the imagery sessions and 304 for the resting-state scans.

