##### Control scans:

The control scans without neurofeedback will be implemented in the same way as described in the neurofeedback paradigm, but a horizontal white line instead of a red or blue bar will be presented for 8 s after each task block. In other words, subjects will not be shown the right insula-dorsomedial frontal cortex functional connectivity strength as neurofeedback. Subjects will know that they will not receive neurofeedback on their performance during control scans. There will be two control scans. The first one will be collected in Visit 2 before the neurofeedback scans and the last one will be collected in Visit 4. The difference in performance between the first and last control scan will serve as a measure of learning.

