### **2.5.1.2.3. Real-time Functional Connectivity Analysis:**

Previously, we used a silent heartbeat counting task during fMRI (Critchley et al., 2004) to functionally localize the insula and dmFC in a different group of subjects with mild PD (N = 10). Figure 3A shows the average group activations in the insula bilaterally (right>left) and dmFC. Our results are in line with previously reported activations in the insula and dmFC during the heartbeat counting task (Kurth et al., 2010; Simmons et al., 2013; Schulz 2016). We will create a cubic anatomical mask (6 x 6 x 6 mm) centered at the voxel with peak activity in the right insula (peak: x = 44, y = 4, z = 8) and dmFC (peak: x = -4, y = 2, z = 62). These anatomical masks will be created in the standard MNI brain space and then translated into each subject's functional space. Functional scans of each subject will be preprocessed and de-noised as described in Scheinost et al (2013b). The signal time course of the right insula and dmFC masks in a given subject will be computed as the average time course across all voxels within each of these masks. Finally, the time courses will be correlated and the r-values will be Fisher z-transformed. A Matlab program will plot the z-values as a bar and present them as neurofeedback (Figure 3B). The same procedures will be applied to the control scans with one exception: The z-values will be recorded, but not presented to the subjects as neurofeedback. Instead, subjects will see a horizontal white line.

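### The Aim 1 connectivity score has no stated handling of the task-evoked response, so if both masks activate together, a rise in activation in the neurofeedback arm can look like learned coupling

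*Combined protocol and SAP*

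**What the plan says.** Under Neurofeedback Paradigm (section 2.5.1.2.2), subjects imagine for 40 s and then see a bar for 8 s. The window for the score is given as "The right insula-dorsomedial frontal cortex functional connectivity strength will be computed during the 40-s task block". On the number of blocks: "There will be five motor imagery task blocks followed by feedback in each session". In control scans the break is kept but the bar is not: "a horizontal white line instead of a red or blue bar will be presented for 8 s after each task block".

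Section 2.5.1.2.3 averages each mask over its voxels, and then "the time courses will be correlated and the r-values will be Fisher z-transformed". It applies the same procedure to the control scans. Preprocessing and de-noising are given only by citing a real-time fMRI system. The de-noising steps listed in section 2.8.1 concern the resting-state data.

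On the endpoint, Control scans says: "The difference in performance between the first and last control scan will serve as a measure of learning". Section 13 tests this in a 2x2 mixed ANOVA with a group x time interaction.

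Two statements of intent bear on interpretation. Section 1.2 presents a technique that "uses the functional connectivity strength between brain regions, as opposed to the activity in a single brain region". Aim 1 justifies the task by "our preliminary data showing the involvement of the insula (sensation) and dmFC (movement) during kinesthetic motor imagery". The control group's imagery has no motor content (section 2.5.2.1).

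**The concern.** The BOLD signal lags the task by several seconds. The fall caused by an 8-s break therefore reaches its low point at the start of the next imagery block, inside the correlation window, and then climbs back. Two regions that both activate during imagery share that dip and climb, so they correlate over the block even if they have no moment-to-moment coupling. The contribution grows with the size of the activation.

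The comparison between arms need not remove it. Kinesthetic motor imagery is expected to involve both masks, while the comparator was chosen to have no motor content. If activation rises between the two control scans in the neurofeedback arm only, the interaction can be significant with coupling unchanged. Aim 1 would then report that subjects learned to raise connectivity when what rose was regional activation. The choice of a connectivity signal was meant to keep those two apart.

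**Working it through.** **Timing.** Section 2.3 gives "FoV: 224 mm, TR: 2000 ms, TE: 25 ms, flip angle: 90" and 120 acquisitions per imagery scan. 5 × (40 + 8) s / 2 s = 120, which matches. The scan therefore holds only imagery blocks and 8-s breaks, and each correlation uses 40 / 2 = 20 volumes.

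**Assumptions, because the documents give no values.** Double-gamma haemodynamic response; plateau amplitude A in units of noise SD; AR(1) noise of 0.3; true noise correlation ρ of 0 or 0.3; score = mean z over the five blocks (the protocol does not say how the blocks are combined); 22 completers per group, taken from the power analysis; extra between-session SD of the change 0.2.

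**Where the dip falls.** The modelled response in blocks 2–5, as a share of plateau at 0, 2, 4, 6, 8 and 10 s, is 0.03, −0.09, 0.12, 0.55, 0.88 and 1.06. The recovery takes about the first 10 s. The SD of this response over the 20 volumes is s = 0.368, so s² = 0.135.

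**Size of the spurious correlation.** With noise variance 1 and amplitudes A₁ and A₂ in the two masks,

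r ≈ (ρ + A₁A₂s²) / √[(1 + A₁²s²)(1 + A₂²s²)].

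- ρ = 0, equal amplitudes. A = 1: 0.135/1.135 = 0.119, z = 0.12. A = 2: 0.542/1.542 = 0.351, z = 0.37. Simulations gave 0.12–0.13 and 0.37–0.40, and 0.03 at A = 0.5.
- ρ = 0.3, equal amplitudes. A = 0.5, 1, 2 gives z = 0.335, 0.404, 0.613. Simulation gave 0.35, 0.42, 0.65.
- ρ = 0.3, second mask at half amplitude. A₁ = 0.5, 1, 2 gives z = 0.321, 0.353, 0.462.
- ρ = 0.3, one mask only. A₁ = 1, 2 gives z = 0.289, 0.246; the score falls slightly.

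**Effect on the group x time test.** The sampling SD of a five-block mean z is about 0.12 per scan. The SD of change is √(2 × 0.12² + 0.2²) = 0.262, and the SE of the group difference is 0.262 × √(2/22) = 0.079. If activation changes only in the neurofeedback arm and coupling is constant:

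| Activation change | Masks | False difference | Difference / SE | Chance of p < 0.05, by simulation |
|---|---|---|---|---|
| 0.5 to 1 SD | equal | 0.404 − 0.335 = 0.069 | 0.87 | about 15–17% |
| 1 to 2 SD | equal | 0.613 − 0.404 = 0.209 | 2.6 | about 74–81% |
| 0.5 to 1 SD | half | 0.353 − 0.321 = 0.032 | 0.4 | about 6% |
| 1 to 2 SD | half | 0.462 − 0.353 = 0.109 | 1.4 | about 27–32% |

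For 0.25 to 0.5 SD with equal masks the rate is 6%, close to nominal. The ranges reflect separate simulation runs. The SD of change also matters. With zero coupling and equal masks, the 1 to 2 SD shift gives a false difference of 0.40 − 0.13 = 0.27, and the chance of significance is above 99%, 85% and 52% at an SD of change of 0.17, 0.30 and 0.45.

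**What removes it.** Regressing the modelled block response out of both masks brings the false-positive rate to 5–6%. Dropping the first three volumes gives 4–8%. Linear detrending within the block is not enough: with zero coupling, z is still 0.09 at A = 1 and 0.29 at A = 2.

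**The case against.** The strongest objection is that the mechanism needs conditions the documents do not establish. Both masks must respond in the same direction and by broadly similar amounts. Aim 1 speaks only of involvement, no amplitude is given, and the masks come from a heartbeat-counting task in other subjects. This stands. It is why the half-amplitude figures sit beside the equal-amplitude ones. A reader might infer that stronger imagery activation always raises the score; it does not. If one mask responds, the score slips slightly, and if the masks respond in opposite directions, it falls.

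Second, the de-noising is delegated to a cited source that cannot be seen here. If that source trims block onset or removes the task response, most or all of the effect goes. This stands too. What the documents support is that the plan states no handling, not that none exists.

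Third, the protocol defines connectivity operationally as this correlation, and joint recruitment of two regions is not single-region activity. That is partly a fair choice of estimand. It does not help a reader who takes a positive Aim 1 result as evidence of coupling distinct from activation.

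A reader might also point to medication state, since the morning dose is held and then taken on the day of Visit 4. Both arms follow the same procedure, and section 2.3 places every scan after the dose. The documents do not make this an arm-specific cause.

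**Conclusion.** The concern holds for the plan as written, conditionally. The Aim 1 score has no stated protection against a shared evoked response, and the visual-imagery arm need not cancel that response in the interaction test. If both masks respond equally, the false-positive rate runs from about 15–17% to 74–81% for the two activation shifts in the table. With the second mask at half amplitude it runs from about 6% to 27–32%. It is negligible when activation stays at or below 0.5 noise SD. The upward bias is absent if only one mask responds or if the cited de-noising already deals with the task response. All of these figures rest on assumed amplitude, noise and SD of change.

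A reader might go further and conclude that the score measures activation rather than connectivity, or that a positive Aim 1 result would be false. The documents do not support that, because they give no amplitudes. The supportable statement is that a positive result could not tell the two apart. The resting-state analysis of Aim 2, the motor analysis of Aim 3 and the sample-size basis are not affected.

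**What to change.** Add a sentence to section 2.5.1.2.3 and to Aim 1 in section 13. For the offline Aim 1 analysis, the modelled block response is regressed out of both mask time courses before the block correlations are computed. Alternatively, each block's z is computed from volumes 4–20. The same rule applies to the first and last control scans in both arms. State how the five block values are combined. Report the untrimmed, unadjusted score as secondary, and show the change in mean activation of each mask beside it. If the cited de-noising already includes such a step, say so.

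Leave the real-time feedback signal as it is. That signal is the intervention, and the rationale for the additional experiments in section 1 already reports results from both groups. Changing it now would mean that subjects were trained on two different signals.

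The cost is a little more analysis on scans that are collected anyway. Regression keeps all 20 volumes but takes its shape from the assumed response model. Trimming leaves 17 volumes, so the nominal SE of each block's z rises from 1/√(20 − 3) to 1/√(17 − 3), a factor of √(17/14) = 1.10, or about 10%.

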##### Control scans:

The control scans without neurofeedback will be implemented in the same way as described in the neurofeedback paradigm, but a horizontal white line instead of a red or blue bar will be presented for 8 s after each task block. In other words, subjects will not be shown the right insula-dorsomedial frontal cortex functional connectivity strength as neurofeedback. Subjects will know that they will not receive neurofeedback on their performance during control scans. There will be two control scans. The first one will be collected in Visit 2 before the neurofeedback scans and the last one will be collected in Visit 4. The difference in performance between the first and last control scan will serve as a measure of learning.

### **2.5.1.2.3. Real-time Functional Connectivity Analysis:**

Previously, we used a silent heartbeat counting task during fMRI (Critchley et al., 2004) to functionally localize the insula and dmFC in a different group of subjects with mild PD (N = 10). Figure 3A shows the average group activations in the insula bilaterally (right>left) and dmFC. Our results are in line with previously reported activations in the insula and dmFC during the heartbeat counting task (Kurth et al., 2010; Simmons et al., 2013; Schulz 2016). We will create a cubic anatomical mask (6 x 6 x 6 mm) centered at the voxel with peak activity in the right insula (peak: x = 44, y = 4, z = 8) and dmFC (peak: x = -4, y = 2, z = 62). These anatomical masks will be created in the standard MNI brain space and then translated into each subject's functional space. Functional scans of each subject will be preprocessed and de-noised as described in Scheinost et al (2013b). The signal time course of the right insula and dmFC masks in a given subject will be computed as the average time course across all voxels within each of these masks. Finally, the time courses will be correlated and the r-values will be Fisher z-transformed. A Matlab program will plot the z-values as a bar and present them as neurofeedback (Figure 3B). The same procedures will be applied to the control scans with one exception: The z-values will be recorded, but not presented to the subjects as neurofeedback. Instead, subjects will see a horizontal white line.

## **2.5.2. Procedures for the PD-control group:**

There will be no interference with the medication schedule. Subjects will take their dopaminergic medication as scheduled.

### **2.5.2.1. Imagery Practice Session:**

To control for the imagery components in the PD-neurofeedback group, PD-control subjects will receive a visual imagery-guided relaxation training based on audio scripts. Guided visual imagery will include shapes, colors, spaces, but no motor imagery. Subjects will be informed about the practice and given time to ask questions. Subsequently, audio-recorded relaxation visual imagery scripts will be provided for each subject to practice.

### **2.5.2.2. Scanning:**

#### **2.5.2.2.1. Resting-state fMRI:**

After the routine anatomical scan for localization (5 min), fMRI scans will be collected during resting-state for 10 min. Subjects will be instructed to keep their eyes closed and let their mind wander without focusing on a specific thought.

#### **2.5.2.2.2. Visual Imagery Scans:**

The same experimental paradigm will be followed as described in Section 2.5.1.2.2 for the control scans. Subjects will perform visual imagery in the scanner, but will not receive neurofeedback, instead, will be presented a horizontal white line. The right insula-dmFC functional connectivity will also be calculated in the same way as explained in Section 2.5.1.2.3 for the control scans.

